# 8.2 Frequency and duration of intervention

Subjects are expected to visit the IOPPN for 4 hourly MRI scans of neurofeedback (see flowchart and Figure 1) which will take about 60 minutes each. On the first and the last NF session, the participants will perform a stop signal task to test motor response inhibition. In addition to these 4 visits, they will also have to come to the IOPPN for pre-assessment where they will perform a task battery of cognitive tests (30 min), and which they will have to repeat after the 4 NF sessions at the post-assessments and again after 6 months follow-up. In total, this will require 7 visits. The parents will also have to fill in some behavioural questionnaires about the behaviour of their child and about side effects at the pre-assessment (~ 2 hours) and post assessments (~ 50 min) as well as the follow-up assessment (about 45min). If they agree to it, the parents and the patient will be audio-recorded during their interviews with the Kiddie-SADS. This will be done to assist us in the reliability of the assessment, in case a diagnosis is questioned later on. Their refusal of the recording will influence not their inclusion in the study.

# 8.3 Intervention records

n/a as this is not a drug trial

# 8.4 Subject Compliance.

n/a as this is not a drug trial

#### 8.5 Study adherence

n/a as this is not a drug trial

#### 8.6 Concomitant Medication

Those patients who are on stimulant medication, may be asked to be taken off their psychostimulant medication 24-hours before the pre-, post-, and follow-up assessment, if it is feasible and if the clinical needs do not override this. (I.e. not to take the medication on the day of the assessments) However, this is not mandatory, this decision will be made by the patient and the parent/guardian, and the patient's clinical needs will override this option. If the patient cannot be taken off medication for the assessments, they can still participate in the study.

For ADHD children to take the medication off for a day is perfectly safe and is commonly done in ADHD research, as the drug wears off within 24 hours and can easily be taken off for a day for this reason. It is common practice in the UK to give children who are on stimulant medication a "drug holiday" over the weekend or on holidays, and it is even recommended as it may prevent the child to develop a tolerance to the drug (when it no longer works). However, as stated above, we will only ask those families who already occasionally take the child off drugs and who know that the child is perfectly manageable without his medication to do this.

For all other timepoints (i.e. the treatment itself), they do not have to come off their medication, but they will be asked to not change their usual medication regime for the duration of the 2 weeks of the NF training. Patients on non-stimulant medication for ADHD will not be asked to be taken off medication at any stage of the study (because, unlike for stimulant medication where the washout is 24 hours, the wash-out of non-stimulant medication is over two weeks and this would not be feasible).

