# 6. Background & Rationale

Attention deficit hyperactivity disorder (ADHD) children have age-inappropriate problems with inattention, hyperactivity and impulsiveness. The most efficacious current treatment is with psychostimulants, which is effective in 70% of children. However, psychostimulants are associated with long-term adverse effects such as reduced growth, irritability, loss of appetite, tremor, sleep and vegetative disturbances (Greenhill et al., 2001; Jensen et al., 2007). There is also some addictive potential of psychostimulants. Furthermore, nothing is known on the long-term effects of psychostimulants. The last decade has shown an escalating rate of stimulant prescription for ADHD with a net drug costs to the NHS in 2010 of £25m and about £30m for health professional, social and educational time. This escalating prescription rate has raised concerns about the unknown long-term effects on the developing brain. Importantly, recent studies have shown limited long-term effects of psychostimulants beyond 1-2 years, despite the fact that currently stimulants are given to ADHD patients long-term, well into adolescence and adulthood. We and others have shown that the brain adapts to the medication which would explain the limited longer-term effects. In conclusion, adverse effects of psychostimulants, lack of evidence for long-term benefits, and potentially long-term negative effects on brain development make the development of a non-pharmacological treatment for ADHD with no side effects highly desirable to parents, clinicians and patients.

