# 7.2 Trial Design

Double-blind, parallel-group, randomised placebo-controlled trial.

We will test the superiority of the real-time fMRI neurofeedback of rIFC over the sham-NF.

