# **10. Selection and Withdrawal of Subjects**

#### 10.1 Inclusion Criteria

One hundred male children/adolescents with ADHD, 10-18 years, medication-naïve or on stable medication, recruited from local clinics, meeting DSM-5 criteria for ADHD using ADHD Diagnostic Interview and rating scales.

- Age range: 10-18 years

- Gender: male

- Meeting DSM-5 diagnosis of ADHD, combined type or inattentive type.

- Score above clinical cut-off for ADHD/ADD on the Schedule for Affective Disorders and Schizophrenia, ADHD module (K-SADS) (Kaufman et al., 1996).

- Score about clinical cut-off for ADHD/ADD on the short forms of the Conners Parent Rating Scales (CPRS/CTRS) (Conners et al., 1998a, b).

The electronic version of this document is the latest version. It is responsibility of the individual to ensure that any paper material is the current version. Printed material is uncontrolled documentation.

- Patients will be either non-medicated (or medication naïve) or on their usual stable medication without change in regime during the 2 weeks of NF training. Only for the prepost and follow-up assessments, if they have agreed to it, they will be taken off stimulant medication.

- IQ > 80 as tested on the 4 subtests of the WASI (Wechsler, 1999) that assesses intellectual ability of individuals aged 6 years and over. Administration of 4 subtests takes ~ 40 minutes, and produces a full-scale IQ score.

Comorbidity with other disorder will be allowed except the ones outlined below under exclusion criteria

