# **11. Trial Procedures**

The following procedure will be followed in this study:

1. The participant will express interest in the study either in response to an advertisement (attached to this proposal), or through information provided by their clinicians at CAMHs or through Trust Consent for Contact (C4C) mechanisms.

2. The participant and the parents will then be sent a copy of the information sheet describing the research study and additional information on the methodologies used. They will receive comprehensive information about the study and the type of screening questions that they will be required to answer on a consent form on the day of the study at least 24 hours before the appointment.

3. If the participant or the parent contacts one of the researchers (by telephone, email, or in person) to receive further information, s/he will be given the opportunity to ask any questions about the study, and to take more time to think about it if they so wish. If they express interest in participating in the study, we will take their contact details to arrange a convenient appointment time.

4. In the week prior to the first testing session, participants will come to the Institute of Psychiatry, Psychology and Neuroscience to complete the IQ testing and to fill in any questionnaires that relates to the main experiment (clinical questionnaires will be filled out by the parents). This visit will also provide the volunteer and his/her parent with an opportunity to ask questions about the study and to familiarise themselves with the study protocol and the facilities. The children will also have to perform a computer test battery that measures attention, inhibition and timing skills.

All participants will be randomly allocated to an experimental (fMRI-NF) and a control group (sham fMRI-NF). The two groups will be matched for age and medication status.

5. At the beginning of any experimental session, the researcher will explain the procedure in detail. Participants will be scanned 4 times in a new GE MR750 3T scanner (General Electrics Milwaukee, USA) for 60min.

Patients will be randomly allocated to active (N = 50) or control groups (N = 50) stratified by age and medication status.

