The active group will be trained to upregulate right inferior frontal lobe activation throughout 14 RT-fMRI-NF runs (7.5 min each, 2-5 sessions per scan), totalling 4 fMRI sessions of 60 minutes over two weeks. In order to prove specificity of NF effects, the control group will have the exact same procedure, but will obtain non-contingent NF from the NF data of one of the active participants.

6. NF sessions (60 min) will consist of 4 runs of each of six activation (upregulation) blocks (40s each), separated by 7 baseline blocks (relaxation/no upregulation), starting and ending with a baseline block (ABABABABABA). The fMRI interface system (provided by [name], Laureate Institute for Brain Research, USA) transfers the images from the MRI

scanner to an external workstation as soon they are reconstructed. Images are then preprocessed using AFNI (afni.nimh.nih.gov/afni), which has built-in real-time capacities. An image mask composed of preselected regions of interest (ROIs) is then applied to the preprocessed images in order to extract the mean neural activity in each selected region. As a new brain volume is acquired every repetition time (2s in this study), AFNI calculates a new set of values for each ROI. The values for each ROI are then sent to a second PC, where they are combined to generate a running time-series for the feedback signal. Finally, this feedback signal is displayed within the scanner in a child-friendly manner. We will present as feedback to the participants their brain activation of rIFG (sham-feedback in controls), using a graphical representation of a rocketeer moving towards the sky, passing through clouds, and ultimately reaching some planets every time they managed to increase the activation of the target region.

Participants cannot easily verbalise the most efficient strategies for successful NF and it is hence more efficient to let participants find their own strategy rather than prescribing one (Birbaumer et al., 2009). The activation will be evaluated in real-time, after each fMRI acquisition, by using the latest reconstructed dataset, i.e. the brain activation during the last 2 seconds.

7. After the last session, the children will be asked to do again the computerised tests of attention, inhibition and timing to test whether they have improved in these skills after the training. The parents also will have to fill in the clinical questionnaires and the side effects scale.

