#### 12.3 Procedures for Assessing Efficacy Parameters

The efficacy measures are parent rated behaviour scales for ADHD behaviours which will be filled in by the parents before and after the treatment and at follow-up assessment.

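### The request to keep medication unchanged covers only the two training weeks, but the primary ADHD-RS change starts earlier and ends later

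*Protocol*

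**What the plan says.** Protocol 8.6 deals first with an optional 24-hour stimulant withdrawal before the pre-, post- and follow-up assessments. For all other timepoints, which it glosses as the treatment itself, children need not come off medication, but "they will be asked to not change their usual medication regime for the duration of the 2 weeks of the NF training". The medication bullet in 10.1 admits children who are non-medicated or "on their usual stable medication without change in regime during the 2 weeks of NF training".

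The primary efficacy measure (sections 12 and 12.1) is the ADHD-RS. Section 12.3 says that the efficacy scales are "filled in by the parents before and after the treatment and at follow-up assessment". The timing of those ratings is set elsewhere:

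- **Before training.** Section 11, step 4: "In the week prior to the first testing session, participants will come to the Institute of Psychiatry, Psychology and Neuroscience" for IQ testing, questionnaires and the computer tests. The same step has the parents complete the clinical questionnaires.
- **After training.** Section 8.2 makes the assessments additional to the four scan visits, with the cognitive battery repeated "after the 4 NF sessions at the post-assessments and again after 6 months follow-up. In total, this will require 7 visits". Section 11, step 7 gives only the order: "After the last session, the children will be asked to do again the computerised tests", with the parents completing the clinical questionnaires at that point too.

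Section 6 describes the strength of the concomitant treatment: "The most efficacious current treatment is with psychostimulants, which is effective in 70% of children".

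**The concern.** The hold on medication and the interval over which the primary outcome is measured should match, and they do not. A regime change between the pre-assessment and the first scan, or between the last scan and the post-assessment, complies with 8.6 but lies inside the ADHD-RS change. By the protocol's own account stimulants are the strongest treatment available, so such a change can move a child's score for a reason unrelated to neurofeedback.

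There is also a gap in who is addressed. The 8.6 request is about a usual regime and follows wording about not having to come off medication. It does not name the non-medicated child who starts treatment.

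At stake is the precision of the primary comparison. The sample size gives about 80% power with 45 evaluable children per group, so there is little slack at that number.

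**Working it through.** **1. Count the visits.** One pre-assessment + 4 scan visits + one post-assessment + one 6-month follow-up = 7, which is the total stated in 8.2. The pre- and post-assessments are therefore not on scan days. The flowchart in 7.3 agrees: Baseline and Endpoint are separate columns from Visits A to D.

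**2. Compare the two windows.** The hold is 2 weeks = 14 days. The ADHD-RS interval is (0 to 7 days before training) + 14 days + (days to the post-assessment, not stated).

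| Gap before first scan | Gap after last scan | Interval | Share covered by the hold |
|---|---|---|---|
| 3 days (assumed) | 0 (assumed) | 17 days | 14/17 = 82% |
| 7 days (upper limit, section 11) | 0 (assumed) | 21 days | 14/21 = 67% |
| 7 days (upper limit, section 11) | 7 days (assumed) | 28 days | 14/28 = 50% |

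Only the 7-day limit before training comes from the protocol. The gap after training is unknown, so the last row is illustrative.

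**3. Look for anything else that closes the gaps.** Stable medication is required at entry (synopsis, 10.1), but no period is attached to the word, and the only no-change period given is the two training weeks. The 24-hour withdrawal is optional, applies only to stimulants and does not fix the underlying regime. Nothing else in the protocol extends the hold.

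**4. Reproduce the planned power.** Inputs from 14.1: effect size 0.6, p < 0.05, 80% power. Two-sided testing is assumed, because the protocol does not state it. A two-sample t-test needs 44.6, so 45 per group, and 45/0.9 = 50 allows for 10% drop-out. Both match the protocol. Power at 45 per group is 80.4%.

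**5. Add noise from regime changes.** The documents give neither a rate of change nor its effect, so both are assumptions. Let a share p of children in each arm change regime in a gap, each moving the ADHD-RS change by d SD up or down with equal chance. Then variance = 1 + p·d², and the standardised effect = 0.6/√(1 + p·d²).

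| p | d | Variance | Effect size | Power, 45 per group |
|---|---|---|---|---|
| none | – | 1.000 | 0.600 | 80.4% |
| 2% | 0.5 | 1.005 | 0.599 | 80.2% |
| 5% | 0.5 | 1.0125 | 0.596 | 79.9% |
| 10% | 0.5 | 1.025 | 0.593 | 79.4% |
| 5% | 1.0 | 1.05 | 0.586 | 78.4% |
| 10% | 1.0 | 1.10 | 0.572 | 76.5% |

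The loss runs from 0.2 to 3.8 percentage points.

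**The case against.** The best reply is that little is exposed.

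- **Stability at entry.** Children must be on stable medication or none, and a child whose regime changes days before the first scan is hard to call stable. This has some force before training, although stability is undefined. It has none for the days after the last scan.
- **Worst-case gaps.** Seven days is an upper limit, and the post-assessment may follow within days. That is true, and it is why no figure is claimed for the later gap.
- **Assumed size.** A loss of nearly 4 points needs 10% of children selected as stable or non-medicated to change within short gaps, each by a full SD. With the pilot's 5% drop-out, about 47 per group would remain. Power would then be 82.1% without the noise and 80.2% at p = 5%, d = 1.0, and only the extreme corner falls clearly below 80% (about 78%). This stands: the top of the range is not the expected loss.
- **No bias.** Section 7.2 describes a "Double-blind, parallel-group, randomised placebo-controlled trial", and 10.4 stratifies by medication status. Nothing in the protocol gives a reason for changes to differ by arm. This also stands.
- **Non-medicated children.** The 10.1 bullet takes medicated and non-medicated children together and could be read as covering a new start. The 8.6 request does not say so.
- **Handled elsewhere.** The flowchart lists a medication form, which may record changes, and their analysis may be set out in the SAP. But what families are asked to do is trial conduct, fixed in 8.6 and 10.1, and an analysis plan cannot lengthen the request.

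**Conclusion.** The mismatch is real, and its importance is minor. The hold stops short of the primary outcome interval at both ends: by up to 7 days before training, and by an unstated number of days after it. The expected effect is a slightly larger variance in the ADHD-RS change, with no expected bias in the comparison and no change to any sample size figure. The power loss of 0.2 to 3.8 points rests wholly on assumed rates and shifts, and the lower part of that range is the more plausible for children selected as stable. It is worth correcting because the protocol states a definite window that is too short, and correcting it costs very little.

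**What to change.** **Section 8.6.** Ask families not to change the ADHD medication regime from the pre-assessment to the post-assessment, and ask families of non-medicated children not to start medication in that period. State that clinical need overrides the request and that the optional assessment-day stimulant withdrawal is excepted.

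**Section 10.1.** Match the bullet, in terms that can be judged before allocation. Suggested text: *non-medicated or on a stable regime at pre-assessment, with no change planned up to the post-assessment.* The present bullet makes eligibility depend on what happens during training, which cannot be known at entry.

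**Cost.** The change is to wording only, with no new visit or measure. A medication form is already in the flowchart, although the text available here does not show at which visits it is used. Families would be asked to hold the regime for up to 7 more days before training, plus the days to the post-assessment. It remains a request, so no child is denied a change that is clinically needed.

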# 9. Research environment

The study will be conducted at an academic institution, the Institute of Psychiatry, Psychology and Neuroscience, at King's College London, UK.

# **10. Selection and Withdrawal of Subjects**

#### 10.1 Inclusion Criteria

One hundred male children/adolescents with ADHD, 10-18 years, medication-naïve or on stable medication, recruited from local clinics, meeting DSM-5 criteria for ADHD using ADHD Diagnostic Interview and rating scales.

- Age range: 10-18 years

- Gender: male

- Meeting DSM-5 diagnosis of ADHD, combined type or inattentive type.

- Score above clinical cut-off for ADHD/ADD on the Schedule for Affective Disorders and Schizophrenia, ADHD module (K-SADS) (Kaufman et al., 1996).

- Score about clinical cut-off for ADHD/ADD on the short forms of the Conners Parent Rating Scales (CPRS/CTRS) (Conners et al., 1998a, b).

The electronic version of this document is the latest version. It is responsibility of the individual to ensure that any paper material is the current version. Printed material is uncontrolled documentation.

- Patients will be either non-medicated (or medication naïve) or on their usual stable medication without change in regime during the 2 weeks of NF training. Only for the prepost and follow-up assessments, if they have agreed to it, they will be taken off stimulant medication.

- IQ > 80 as tested on the 4 subtests of the WASI (Wechsler, 1999) that assesses intellectual ability of individuals aged 6 years and over. Administration of 4 subtests takes ~ 40 minutes, and produces a full-scale IQ score.

Comorbidity with other disorder will be allowed except the ones outlined below under exclusion criteria

# 10.2 Exclusion Criteria

- IQ < 80 (Wechsler et al., 1999).

- Comorbidity with schizophrenia, Bipolar disorder, autism, learning disability, severe depression with current suicidal behaviour (as assessed by clinician). Problems with mood, anxiety and depression will be allowed as long as they are not the primary diagnosis.

- Neurological problems, i.e. a history of severe neurological illness, e.g. brain tumour, epilepsy or a history of symptomatic seizures, polyneuropathy etc.

- Substance abuse history

- Contraindication to fMRI. i.e., previous implantation of metallic material, pacemaker, implanted medication pumps, neural stimulators, claustrophobia.

- Unable to give informed consent by the patient or the parent/primary caregiver.

#### 10.3 Selection of Participants

Patients will be recruited through Child and Adolescent Mental Health Services, via advertisement, social media, parent support groups, community paediatrics, and paediatrics and general practitioner settings as well as via Trust Consent for Contact mechanisms.

# 10.4 Randomisation Procedure / Code Break

The ADHD children (non-medicated or on stable medication) will be randomized to sham or real fMRI-NF of rIFC, 50 in each group. Stratification factors will include medication status (non-medicated/stable) and age. Patients will be randomly assigned in a 1:1 ratio with varying block size to either the experimental (real fMRI-NF) or the control (sham-fMRI-NF) groups. This assignment will be realized by a computer-generated, web-based tool provided by the Clinical Trials Unit of the IOPPN, KCL.

#### 10.5 Withdrawal of Subjects

There is no evidence for side or adverse effects of the therapy, hence withdrawal due to adverse effects are not expected. Therapy will be discontinued if

- the participant decides they no longer wish to continue
- recommended by the investigator

Should a patient decide to withdraw from the study, the reason for withdrawal will be recorded as detailed as possible.

Participants who wish to withdraw from therapy will be asked to confirm whether they are still willing to provide the study specific data at visits that were completed.

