8. After 6 months (after the training) the parents will be asked to fill in (or answer by telephone) the ADHD severity questionnaire and the child will have to repeat the cognitive test battery one more time.

9. The participants will receive up to £180. We will give them tokens for each visit throughout the 2 week training. They will receive money in exchange for the tokens at the end of the training and at the follow-up assessment. We will also reimburse their travel costs.

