# 12.1 Primary Efficacy Parameters

ADHD symptoms as measured on the ADHD-Rating Scale (ADHD-RS). (Dupaul et al. 1999).

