#### 14.3 Analysis

A description of the statistical methods to be employed, including timing of any planned interim analyses should also be provided The level of significance that is to be used in each trial analysis must be stipulated, together with the procedure(s) for accounting for any missing, unused, and spurious data. Procedures for reporting any deviation from the original statistical plan should be described and justified. The data set for any analysis must be clearly stipulated (e.g. "all subjects", "randomised subjects", "intent to treat") and the population(s) should be clearly defined. Define the trial stopping rules if appropriate.

For all analyses, repeated measures ANOVAs will be conducted with TIME as within-subject factor and GROUP as between subject factor. Supplementary analyses may include parametric correlation analyses (for example Pearson's correlation tests).

The named researchers have substantial and proven experience in these types of analyses, having published and taught extensively.

For missing data, imputations will be used. The individual estimates from the multiply-imputed datasets will then be used to calculate a combined estimate by applying Rubin's Rules [Little and Rubin, 2002].

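### Section 10.5 makes no provision for collecting the post-treatment or 6-month ADHD-RS from a child who stops neurofeedback early, so these primary outcomes would be imputed when they could be observed

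*Protocol*

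**What the plan says.** Section 10.5 gives two grounds for stopping therapy: "the participant decides they no longer wish to continue", or the investigator recommends it. For withdrawal from the study it requires the reason to be recorded. For withdrawal from therapy it says the participants will be asked "whether they are still willing to provide the study specific data at visits that were completed". Nothing more is said about data after stopping. That question is put only to participants who wish to withdraw, so a child stopped on the investigator's recommendation has no data rule.

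The primary efficacy measure in Section 12.1 is "ADHD symptoms as measured on the ADHD-Rating Scale (ADHD-RS". Section 12.3 says the efficacy scales are parent-rated and "filled in by the parents before and after the treatment and at follow-up assessment". Section 11, step 7, fixes the post-treatment assessment: "After the last session, the children will be asked to do again the computerised tests", with the parent questionnaires alongside. Step 8 says that at 6 months "the parents will be asked to fill in (or answer by telephone) the ADHD severity questionnaire". Section 7.1.2 names the parent ADHD-RS as a 6-month outcome.

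Section 14.1 needs 45 children per group and enrols 50 to allow for up to 10% drop-out. It reports 5% drop-out in the pilot and 6% to 10% in the group's earlier repeated-scan medication studies. Section 14.3 states "For missing data, imputations will be used", with estimates combined by Rubin's Rules.

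**The concern.** The data question in Section 10.5 looks back to visits already made. A child who stops after the first training visit has by then supplied a baseline assessment and one scan visit. Followed literally, the protocol leaves that child without the primary outcome at either later time point.

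An analysis plan cannot repair this afterwards. It can choose an imputation model and an analysis set, but it cannot recover a rating that nobody requested. If children who stop differ in outcome from those who continue, and stopping is not balanced between real and sham feedback, the randomised comparison comes to rest on an assumption about the unobserved ratings that the trial data cannot test. The loss is also avoidable, because the rating comes from a parent and does not depend on the child being scanned.

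**Working it through.** **1. The plan's own sample size (Section 14.1).** Inputs: effect size 0.6, power 80%, p < 0.05. Sidedness is not stated; two-sided reproduces the figure.
- Normal approximation: n = 2 × (1.960 + 0.842)² / 0.6² = 43.6, so 44 per group.
- Two-sample t-test: 44.6, so 45 per group, as stated.
- Drop-out allowance: 45 / (1 − 0.10) = 50 per group, as stated.

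The sample size is not in error. It treats drop-outs as lost to the comparison.

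**2. Can stopping occur after randomisation?** Section 8.1 puts two feedback runs in the first scan visit, so allocation must precede it. Section 13.1 expects the first scan to show a child whether four scans are acceptable to him. The mock scanner may screen out some children before that, but those who find the real scanner intolerable leave after allocation.

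**3. Is there any route to a later rating?**
- Section 10.5: a question about data from past visits, put only to those who wish to withdraw.
- Section 11, step 7: ratings follow the last session; early stopping is not addressed.
- Section 11, step 8, and Section 12.3: ratings at 6 months and after treatment, in general terms; early stopping is not addressed.
- Section 14.3: missing values are imputed.

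No section requests the rating from a child who has stopped, and none forbids it.

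**4. How many children?** 100 × 0.05 = 5 at the pilot rate and 100 × 0.10 = 10 at the planned maximum.

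**5. Illustrative size of bias.** This is for a complete-case comparison, which is not the planned analysis. Let a proportion p of an arm stop, and let stoppers score δ SD worse than those who continue in the same arm. The mean of everyone randomised to that arm is then p × δ worse than the mean of its completers. With the same δ in both arms, the between-arm bias is δ × (p₁ − p₂), where p₁ and p₂ are the stopping proportions in the two arms. With δ = 1 (an assumption; the protocol gives no figure):

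| Stopping, one arm vs the other | Bias | Share of 0.6 |
|---|---|---|
| 10% vs 10% | 1 × (0.10 − 0.10) = 0 | 0% |
| 10% vs 5% | 1 × (0.10 − 0.05) = 0.05 SD | 0.05 / 0.6 = 8% |
| 10% vs 0% | 1 × (0.10 − 0) = 0.10 SD | 0.10 / 0.6 = 17% |

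A smaller deficit scales these down: at 10% versus 0%, δ = 0.3 gives 0.03 SD and δ = 0.6 gives 0.06 SD. The bias favours the arm with more stopping.

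**The case against.** The strongest reply is that the protocol does not bar later collection. Section 10.5 distinguishes leaving the study from leaving therapy, and its data question is awkwardly drafted: it opens by looking forward and ends by looking back. Section 12.3 and step 8 of Section 11 set the ratings without restricting them to children who finish. A reader might infer that the protocol ends data collection when training stops, so that outcomes are lost by design. The documents do not support that. They support only the absence of a provision, and that part of the concern stands.

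Four other strong readings should also be set aside.
- *The trial estimate is biased by 0.1 SD.* That figure needs 10% stopping in one arm, none in the other, a 1 SD deficit and a complete-case analysis. Section 14.3 plans multiple imputation.
- *Imputation would use baseline data alone, or only children who finished.* Section 14.3 names no model or variables, and the Section 7.3 flowchart lists training-phase records that might inform one. The model and the analysis set may properly sit in an analysis plan that is not among the documents.
- *Following stoppers raises power.* At an effect of 0.6, t-test power is 80.4% with 45 per group and 84.4% with 50, but only if stoppers show the full effect. If they gain nothing (assumed), the effect in all randomised is 0.6 × 0.95 = 0.57 to 0.6 × 0.90 = 0.54, and power with 50 per group is 80.6% to 76.2%. The case for follow-up does not rest on power.
- *Stopping is known to be informative.* The documents do not show this. Section 14.1 reports that the pilot was well tolerated, and Section 10.5 records reasons for study withdrawal, which would allow a partial check.

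**Conclusion.** The concern holds as a gap in follow-up. The protocol does not ask for the primary outcome after a child stops training, and a literal reading leaves that outcome to be imputed. The scale is modest: about 5 to 10 of 100 children at the protocol's own drop-out rates. Under the complete-case illustration, the between-arm bias runs from 0 to 0.1 SD. That range assumes a 1 SD deficit, equal in both arms, and stopping of at most 10% in either arm. The bias under the planned imputation cannot be computed without the model. What can be said is that an observed rating removes the need for an untestable assumption about that child, and that no analysis plan can supply the rating later. This is a cheap improvement that the sponsor should make. It is not an error that invalidates the design.

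**What to change.** In Section 10.5, separate stopping training from withdrawing consent for data collection. State that every randomised family whose child stops training, for whatever reason and including on the investigator's recommendation, will be asked to complete the ADHD-RS at the scheduled post-treatment and 6-month times, by form or telephone, unless they withdraw consent for further data. Amend step 7 of Section 11 so that the post-treatment parent rating is due at its scheduled time whether or not the child reaches the last session. The change concerns data collection only and leaves the decision to stop training as it is.

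The cost is a minor amendment with matching consent wording, and one or two questionnaires or calls for about 5 to 10 families. The sample size does not change.
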